6.5.4.2 Anaphylaxis

Anaphylaxis should lead to immediate interruption of ongoing infusion, and to permanent discontinuation of both SAR444245 and pembrolizumab being administered.

Management should be prompt and may include but is not limited to administration of epinephrine, IV fluids, antihistamines, oxygen, vasopressors, corticosteroids, as well as increased monitoring of vital signs as medically indicated, until the participant recovers (see guidelines) (26, 27, 28).

6.5.4.3 Fever, flu-like symptoms and cytokine-release syndrome (CRS)

Fever can frequently happen with infusion of IL-2 and may possibly evolve into flu-like symptoms or could be an early manifestation of CRS. Fever or flu-like symptoms should be graded according to CTCAE V5.0 and managed according to institutional standards.

Cytokine-release syndrome should be graded as per American Society for Transplantation and Cellular Therapy (ASTCT) criteria integrated with central laboratory cytokine results, and managed per guidelines in [Table 5](#). If any grade of CRS is suspected, sites should make every effort to draw an additional blood sample for cytokines levels (by central laboratory), prior to the administration of tocilizumab, as well as for C-reactive protein (CRP) and ferritin (by local laboratory).

Sites should have at least 2 full doses of tocilizumab available, or alternative therapies per site practice in CRS management, and access to an intensive care unit (ICU), in case participants develop CRS.

Guidelines for management of CRS according to severity grading are provided in [Table 5](#). ASTCT CRS consensus grading scale is provided in Section 10.11 of the master protocol.

Table 5 - Guidelines for the management of suspected cytokine release syndrome (CRS)

Event severity (ASTCT CRS Consensus Grading)	Recommended SAR444245 dose modification and supportive care guidelines
Grade 1 
 • Fever (Temperature $\geq 38^{\circ}\text{C}$)^b • No hypotension • No hypoxia 	No dose modification of SAR444245^a. Appropriate symptomatic treatment may include but is not limited to IV fluids (care should be taken to not excessively hydrate if evidence of vascular leak), antihistamines, NSAIDs and acetaminophen. Close direct monitoring of the participant's clinical status. Clinical and laboratory monitoring should initially be performed daily, then less frequently as the participant improves.
Grade 2 
 • Fever^b (Temperature $\geq 38^{\circ}\text{C}$) • Hypotension not requiring vasopressors • and/or^c hypoxia requiring low-flow nasal cannula^d or blow-by. 	Temporarily interrupt of SAR444245, if event occurs during infusion Additional appropriate medical therapy may include but is not limited to IV fluids (care should be taken to not excessively hydrate if evidence of vascular leak), antihistamines, NSAIDs and acetaminophen. Monitoring of vital signs, cardiac and other organ functions closely as medically indicated should be increased until the participant recovers. Transfer to ICU may be required. For participants with comorbidities, older age, or with oxygen requirement, hypotension, or participants in whom symptoms (eg, high grade fever) that do not respond to antipyretics within 72 hours treatment with corticosteroids and/or tocilizumab or alternative therapies per site practice in CRS management should be considered, as per guidance for Grade 3 events. SAR444245 may be resumed when clinical symptoms have resolved or improved to Grade 1 and corticosteroid taper. No dose modification is required but decreasing to half the infusion rate can be considered.
Grade 3 
 • Fever^b (Temperature $\geq 38^{\circ}\text{C}$) • Hypotension requiring a vasopressor with or without vasopressin • And/or^c hypoxia requiring high-flow nasal cannula^d, face mask, nonrebreather mask, or Venturi mask 	If CRS grade 3, SAR444245 should be temporarily withheld, and subsequent treatment should be resumed only when symptoms have resolved or improved to Grade 1. SAR444245 can be either restarted at \blacksquare $\mu\text{g}/\text{kg}$ or permanently discontinued, as clinically indicated.
Grade 4 Life-threatening consequences; urgent intervention indicated 
 • Fever^b (Temperature $\geq 38^{\circ}\text{C}$) • Hypotension requiring multiple vasopressors (excluding vasopressin) 	If CRS Grade 4, SAR444245 should be permanently discontinued, as clinically indicated. If CRS Grade 3 or Grade 4, IV corticosteroids should be initiated (outside of the context of CAR-T cells, corticosteroids alone maybe initiated in first intention) and tocilizumab or alternative therapies per site practice in CRS management should be considered, and/or epinephrine and/or other vasopressors should be administered as needed. Participants with severe CRS may require management in intensive care setting, with monitoring of clinical status and laboratory tests performed at least daily. As the participant improves, the intensity of the monitoring and setting can be decreased, but the participant should not be discharged from the

Event severity (ASTCT CRS Consensus Grading)	Recommended SAR444245 dose modification and supportive care guidelines

 And/or ^c hypoxia requiring positive pressure (eg, CPAP, BiPAP, intubation and mechanical ventilation) 	
hospital until clinically stable. Corticosteroids can then be administered IV or orally every 8 hours for up to 3 days, then tapered over 4 days. In general, tapering of steroids can start when vasopressors and high-flow oxygen are no longer needed.
 
CRS is considered resolved when there is sustained resolution of fever and there is no longer a need for oxygen supplementation to relieve hypoxia nor vasopressors to maintain blood pressure; however, normalization of temperature alone does not define resolution of CRS.
 
If no clinical improvement in oxygenation, hypotension, fever, and other CRS manifestations is observed within 24 to 72 hours, management for persistent or worsening CRS should be initiated. Re-evaluation for other contributing conditions should be done, such as infection, cardiac, thromboembolic and other complications. Intravenous Tocilizumab at 8 mg/kg (for participants weighing ≥ 30 kg), or alternative therapies per site practice in CRS management, should be administered, and steroids should be administered concurrently. If still no improvement in oxygenation, hypotension, fever and other manifestations is observed after the first dose of tocilizumab, or alternative therapies per site practice in CRS management, it may be repeated after an interval of at least 8 hours and should not exceed 4 doses in total.
 
For participants with severe CRS who fail to improve after repetitive treatment with both tocilizumab or alternative therapies per site practice in CRS management and steroids, alternative options should be discussed with clinical site specialists

a Information for preparation and storage of SAR444245 is provided in the pharmacy manual.

b Fever is defined as temperature $\geq 38^{\circ}\text{C}$ not attributable to any other cause. In patients who have CRS then receive antipyretic or anticytokine therapy such as tocilizumab or alternative therapies per site practice in CRS management or steroids, fever is no longer required to grade subsequent CRS severity. In this case, CRS grading is driven by hypotension and/or hypoxia.

c CRS grade is determined by the more severe event: hypotension or hypoxia not attributable to any other cause. For example, a patient with temperature of 39.5°C , hypotension requiring 1 vasopressor, and hypoxia requiring low-flow nasal cannula is classified as Grade 3 CRS.

d Low-flow nasal cannula is defined as oxygen delivered at ≤ 6 L/minute. Low flow also includes blow-by oxygen delivery, sometimes used in pediatrics. High-flow nasal cannula is defined as oxygen delivered at > 6 L/minute.

Abbreviations: AE = Adverse event; ASTCT=American Society for Transplantation and Cellular Therapy; BiPAP= Bilevel Positive Airway Pressure; CPAP= Continuous Positive Airway Pressure; CRS= cytokine release syndrome; ICU=intensive care unit; IL = Interleukin; IMP=investigational medicinal product; IV = Intravenous; NSAIDs=Non-steroidal anti-inflammatory drugs.

6.5.4.4 Immune-related adverse events

AEs associated with pembrolizumab exposure may represent an immunologic etiology. These immune-related AEs (irAEs) may occur shortly after the first dose or several months after the last dose of pembrolizumab treatment and may affect more than one body system simultaneously. Immune-related AEs are thought to be caused by unrestrained cellular immune responses directed at the normal host tissues. Therefore, early recognition and initiation of treatment is critical to reduce complications. Based on existing pembrolizumab clinical study data, most irAEs were reversible and could be managed with interruptions of pembrolizumab, administration of corticosteroids and/or other supportive care.

Investigators must be extremely vigilant and be ready to intervene early in the management of irAEs because the onset of symptoms of irAEs (eg, pneumonitis) may be subtle. For suspected irAEs, adequate evaluation should be performed to confirm etiology or exclude neoplastic,

infectious, metabolic, toxin, or other etiologic causes. Additional procedures or tests such as bronchoscopy, endoscopy, skin biopsy may be included as part of the evaluation. Based on the severity of irAEs, withhold or permanently discontinue pembrolizumab and/or SAR444245 and administer corticosteroids.

SAR444245 may increase the incidence and severity of these events.

Dose modification and toxicity management guidelines for irAEs are provided in [Table 6](#). Of note, when study interventions are administered in combination, if the AE is considered immune-related, both drugs in the combination should be held according to recommended dose modifications. If a participant experiences several irAEs, the most conservative recommendation should be followed.

The CTCAE V5.0 must be used to grade the severity of AEs.

When SAR444245 or pembrolizumab can be restarted, they should be administered at the initial planned dose and schedule as no modification is allowed:

- If the toxicity does not resolve or the criteria for resuming treatment are not met, the participant must be discontinued from all study drugs.
- If the toxicities do resolve and conditions are aligned with what is defined in [Table 6](#), the combination of SAR444245 and pembrolizumab may be restarted at the discretion of the Investigator. In these cases where the toxicity is attributed to the combination or to SAR444245 alone, re-initiation of pembrolizumab as a monotherapy may be considered after communication with the Sponsor.

Table 6 - Dose modification and toxicity management guidelines for immune-related AEs associated with pembrolizumab and SAR444245

General instructions:

1. Severe and life-threatening irAEs should be treated with IV corticosteroids followed by oral steroids. Other immunosuppressive treatment should begin if the irAEs are not controlled by corticosteroids.
2. Pembrolizumab and SAR444245 must be permanently discontinued if the irAE does not resolve or the corticosteroid dose is not \leq 10 mg/day within 12 weeks of the last pembrolizumab treatment.
3. The corticosteroid taper should begin when the irAE is \leq Grade 1 and continue at least 4 weeks.
4. If pembrolizumab and SAR444245 have been withheld, pembrolizumab and SAR444245 may be resumed after the irAE decreased to \leq Grade 1 after corticosteroid taper.

irAEs	Toxicity grade (CTCAE V5.0)	Action with pembrolizumab and SAR444245	Corticosteroid and/or other therapies	Monitoring and follow-up
Pneumonitis	Grade 2	Withhold ^a	Administer corticosteroids (initial dose of 1 - 2 mg/kg prednisone or equivalent) followed by taper.	Monitor participants for signs and symptoms of pneumonitis.
	Recurrent Grade 2, Grade 3 or 4	Permanently discontinue ^b	Add prophylactic antibiotics for opportunistic infections.	Evaluate participants with suspected pneumonitis with radiographic imaging and initiate corticosteroid treatment.

irAEs	Toxicity grade (CTCAE V5.0)	Action with pembrolizumab and SAR444245	Corticosteroid and/or other therapies	Monitoring and follow-up
Diarrhea/Colitis	Grade 2 or 3	Withhold ^a	Administer corticosteroids (initial dose of 1 - 2 mg/kg prednisone or equivalent) followed by taper.	Monitor participants for signs and symptoms of enterocolitis (ie, diarrhea, abdominal pain, blood or mucus in stool with or without fever) and of bowel perforation (ie, peritoneal signs and ileus). Participants with ≥Grade 2 diarrhea suspecting colitis should consider GI consultation and performing endoscopy to rule out colitis.
	Recurrent Grade 3 or Grade 4	Permanently discontinue ^b		Participants with diarrhea/colitis should be advised to drink liberal quantities of clear fluids. If sufficient oral fluid intake is not feasible, fluid and electrolytes should be substituted via IV infusion.
AST or ALT elevation or Increased Bilirubin	Grade 2 ^c	Withhold ^a	Administer corticosteroids (initial dose of 0.5-1 mg/kg prednisone or equivalent) followed by taper.	Monitor with liver function tests (consider weekly or more frequently until liver enzyme value returned to baseline or is stable).
	Grade 3 ^d or 4 ^e	Permanently discontinue ^b	Administer corticosteroids (initial dose of 1-2 mg/kg prednisone or equivalent) followed by taper.	
Type 1 Diabetes Mellitus (T1DM) or Hyperglycemia	New onset T1DM or Grade 3 or 4 hyperglycemia associated with evidence of β-cell failure	Withhold ^{af}	Initiate insulin replacement therapy for participants with T1DM. Administer anti-hyperglycemic in participants with hyperglycemia.	Monitor participants for hyperglycemia or other signs and symptoms of diabetes.
Hypophysitis	Grade 2	Withhold ^a	Administer corticosteroids and initiate hormonal replacements as clinically indicated.	Monitor for signs and symptoms of hypophysitis (including hypopituitarism and adrenal insufficiency).
Hyperthyroidism	Grade 3 or 4	Withhold ^a or permanently discontinue ^{bf}	Treat with non-selective beta-blockers (eg, propranolol) or thionamides as appropriate.	Monitor for signs and symptoms of thyroid disorders.

irAEs	Toxicity grade (CTCAE V5.0)	Action with pembrolizumab and SAR444245	Corticosteroid and/or other therapies	Monitoring and follow-up
Hypothyroidism	Grade 2, 3, or 4	Continue	Initiate thyroid replacement hormones (eg, levothyroxine or liothyronine) per standard of care.	Monitor for signs and symptoms of thyroid disorders.
Nephritis: grading according to increased creatinine or acute kidney injury	Grade 2	Withhold ^a	Administer corticosteroids (prednisone 1-2 mg/kg or equivalent) followed by taper.	Monitor changes of renal function.
Neurological Toxicities	Grade 3 or 4	Permanently discontinue ^b	Based on severity of AE administer corticosteroids	Ensure adequate evaluation to confirm etiology and/or exclude other causes
Myocarditis	Grade 2, 3 or 4	Permanently discontinue ^b	Based on severity of AE administer corticosteroids.	Ensure adequate evaluation to confirm etiology and/or exclude other causes.
Exfoliative Dermatologic Conditions	Suspected SJS, TEN, or DRESS	Withhold ^a	Based on severity of AE administer corticosteroids	Ensure adequate evaluation to confirm etiology and/or exclude other causes
	Confirmed SJS, TEN, or DRESS	Permanently discontinue ^b		
All Other irAEs	Persistent Grade 2	Withhold ^a	Based on severity of AE administer corticosteroids.	Ensure adequate evaluation to confirm etiology or exclude other causes.
	Grade 3	Withhold ^a or discontinue based on the event ^g		
	Recurrent Grade 3 or Grade 4	Permanently discontinue ^b		

a SAR444245 to be withheld plus pembrolizumab to be withheld corresponds to "cycle delay".

b Permanently discontinuation of full study treatment.

c AST/ALT: >3.0 - 5.0 x ULN if baseline normal; >3.0 - 5.0 x baseline, if baseline abnormal; bilirubin:>1.5 - 3.0 x ULN if baseline normal; >1.5 - 3.0 x baseline if baseline abnormal.

d AST/ALT: >5.0 to 20.0 x ULN, if baseline normal; >5.0 - 20.0 x baseline, if baseline abnormal; bilirubin:>3.0 - 10.0 x ULN if baseline normal; >3.0 - 10.0 x baseline if baseline abnormal.

e AST/ALT: >20.0 x ULN, if baseline normal; >20.0 x baseline, if baseline abnormal; bilirubin: >10.0 x ULN if baseline normal; >10.0 x baseline if baseline abnormal.

f The decision to withhold or permanently discontinue pembrolizumab and SAR444245 is at the discretion of the Investigator or treating physician. If control achieved or ≤Grade 2, pembrolizumab and SAR444245 may be resumed.

g Events that require discontinuation include but are not limited to: encephalitis and other clinically important irAEs (eg. vasculitis and sclerosing cholangitis).

AE(s)=adverse event(s); ALT= alanine aminotransferase; AST=aspartate aminotransferase; CTCAE=Common Terminology Criteria for Adverse Events; DRESS=Drug Rash with Eosinophilia and Systemic Symptom; GI=gastrointestinal; IO=immuno-oncology; ir=immune related; IV=intravenous; SJS=Stevens-Johnson Syndrome; T1DM=type 1 diabetes mellitus; TEN=Toxic Epidermal Necrolysis; ULN=upper limit of normal.

Note: Non-irAE will be managed as appropriate, following clinical practice recommendations.

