6.5 DOSE MODIFICATION

6.5.1 General rules

Dose modification for SAR444245 is permitted according to the guidelines described in this section. Pembrolizumab dose reductions are not permitted. Pembrolizumab treatment may be withheld or discontinued due to toxicity.

Dose modifications different from those stated in the protocol should only be made in consultation with the Sponsor, unless required for immediate participant safety.

Cycle delay (ie, Day 1 should be delayed for all IMPs) is permitted in case of treatment-emergent adverse event (TEAE). Dose modification will be made according to the worst grade of toxicity observed within a cycle. If a participant experiences several toxicities and there are conflicting recommendations, the most conservative recommended dose adjustment should be followed. Once a dose has been decreased, intra-patient re-escalation back to the previous dose level is not permitted.

Administration of the study treatment will be discontinued in the event of a TEAE that persists despite appropriate dose modifications or any other TEAE that, in the opinion of the Investigator, warrants discontinuation.

If any of the IMP components is permanently discontinued, the other IMP component can be continued until disease progression or other criteria as detailed in Section 7.1.1 of the master protocol are met. In this case it is partial permanent discontinuation and the end of treatment (EOT) assessment will be 30 days after the date of the last administration of the remaining IMP. When all IMP components are permanently discontinued it is full permanent discontinuation.

All changes to study treatment administration must be recorded in the electronic case report form (e-CRF).

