6.5.3 General guidelines for the management of treatment-related adverse events

Participants who experience Grade ≥ 3 treatment-related adverse events (TRAEs) at any time of the study (including clinically significant grade 3 laboratory abnormalities as defined in Section 10.3.1 of the master protocol) will be required to cycle delay the IMP, unless specified otherwise in the protocol, and with the exception of the TRAEs resolving within 5 days. After cycle delay, such participants may be considered for treatment resumption once the TRAE resolves or improves to Grade 1 or baseline or is stable and manageable through supportive/medical therapy. Treatment resumption is at the discretion of the Investigator and Sponsor, if thought to be in the best interest of the participant, except when specified otherwise in this protocol, or if the event has required the IMP temporary withheld for more than 84 days from the last scheduled dose.

The cycle delay of treatment for Grade 2 events is left at the discretion of the Investigator unless otherwise specified in this protocol.

No cycle delay of treatment or dose modification is required for Grade 1 events.

Dose reduction for SAR444245 from █ μg/kg to █ μg/kg (or another lower dose recommended by Study Board) may be decided when specified in the protocol or following discussions with the Sponsor.

The final decision on dose modification and/or corrective therapy will be based on the Investigator's judgment, in the best interest of the participant.

Recommended guidelines for the management of specific adverse events including irAE, CRS, vascular leak syndrome (VLS) and IRR are presented in [Section 6.5.4](#).

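### Cohort A: the restart rule after an immune-related event makes no exception for a SAR444245 dose already reduced, so read literally it contradicts the ban on re-escalation

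*Protocol*

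**What the plan says.** All references are to Substudy 01 (Cohort A, SAR444245 plus pembrolizumab) unless stated.

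- **Section 6.5.4.4**, on restarting either drug after an irAE hold: "they should be administered at the initial planned dose and schedule as no modification is allowed". A bullet below adds that, once the toxicity has resolved and Table 6 is satisfied, "the combination of SAR444245 and pembrolizumab may be restarted at the discretion of the Investigator".
- **Section 6.5.1** permits dose modification of SAR444245. For pembrolizumab: "Pembrolizumab dose reductions are not permitted". It then sets the general ban: "Once a dose has been decreased, intra-patient re-escalation back to the previous dose level is not permitted". The sentence before the ban reads: "If a participant experiences several toxicities and there are conflicting recommendations, the most conservative recommended dose adjustment should be followed".
- **Section 6.5.3** says that a SAR444245 reduction "may be decided when specified in the protocol or following discussions with the Sponsor". It also says: "The final decision on dose modification and/or corrective therapy will be based on the Investigator's judgment".
- **Tables 5, 7 and 8** give event-specific routes to a changed dose. After Grade 2 VLS, SAR444245 resumes at a reduced level (Table 8). After Grade 2 neurotoxicity (ICANS), a reduction may be considered (Table 7). After Grade 3 cytokine release syndrome (CRS), "SAR444245 can be either restarted at" a blacked-out dose or stopped for good (Table 5). Grade 3 ICANS has the same two options (Table 7).
- **Table 6** tells the site to withhold, discontinue or continue for each irAE. It never reduces a dose.

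**The concern.** The irAE restart sentence points to the starting dose and gives as its reason that no modification is allowed. Section 6.5.1 does allow SAR444245 to be modified, and some participants may reach their first irAE hold on a reduced dose. Taken at its word, Section 6.5.4.4 would return them to the level that was lowered for toxicity, just after a second toxicity. The same section warns that SAR444245 may make irAEs more frequent and more severe. What is at stake is dosing safety for an individual participant and consistent handling across sites, not the efficacy analysis.

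**Working it through.** The plan states no figure on this point, so the check is a comparison of the text.

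**1. Can a participant be on a reduced dose before an irAE hold?** Yes. Three routes do not depend on any blacked-out figure: Grade 2 VLS, Grade 2 ICANS, and a reduction agreed with the Sponsor. Grade 3 CRS and Grade 3 ICANS are further routes only if the redacted restart dose is below the starting dose, which is an assumption.

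**2. Follow one participant through both rules.**

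| Step | Rule | SAR444245 dose |
|---|---|---|
| Start | Synopsis and Table 2 | 24 µg/kg every 3 weeks |
| Grade 2 VLS, resolved | Table 8 | reduced level (redacted) |
| Later Grade 2 irAE that Table 6 withholds, resolved | Section 6.5.4.4, literal | 24 µg/kg |
| Same event | Section 6.5.1 | not 24 µg/kg |

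The last two rows cannot both be followed.

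**3. Is there an exception anywhere in the irAE material?** None appears in the restart sentence, the two bullets under it, the general instructions above Table 6 or the footnotes below it. The tie-break inside Section 6.5.4.4 covers several irAEs. It does not cover an irAE that follows a reduction for VLS, CRS or ICANS.

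**4. Who is not affected?** Participants never reduced, because Table 6 does not reduce doses. Pembrolizumab, because its dose is never reduced. Cohort C1, because Substudy 03 has no irAE restart section.

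**5. Scale, as illustration only.** With independence assumed, expected participants = 25 × P(earlier reduction) × P(irAE withheld and resolved), and P(at least one) = 1 − (1 − product of the two)^25.

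- The 25 is from Section 9.2. An earlier-reduction rate of 5% to 10% is assumed.
- For the irAE rate, take 4/38 from the NKTR-214 plus nivolumab study (master protocol 2.3.1.3). That study lists 11 hypothyroidism, 2 hyperthyroidism and 2 hyperglycemia events. Table 6 continues treatment through hypothyroidism, which leaves 2 + 2 = 4.
- At 5%: 0.05 × 4/38 = 0.00526; 25 × 0.00526 = 0.13 participants; 12.4% chance of at least one.
- At 10%: 0.10 × 4/38 = 0.01053; 25 × 0.01053 = 0.26 participants; 23.2% chance of at least one.

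These are not bounds. The irAE rate belongs to another IL-2 agent given with another antibody in solid tumours. Table 6 also withholds for pneumonitis, colitis, hepatic, renal and other events outside the three listed types. In the other direction, not all four events need have met the Table 6 thresholds, and the reduction must precede the irAE. The reduction rate could be off either way. The one Grade 3 CRS among 20 participants on SAR444245 plus pembrolizumab in HAMMER occurred at 16 µg/kg, below the dose used here, but without the peri-infusion hydration required here (master protocol 4.3 and 6.1.1).

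**The case against.** The strongest reply is that the protocol already settles the matter. Section 6.5.1 is headed as general rules and its ban is flat, whereas the irAE sentence says should and sits among what Section 6.5.3 calls recommended guidelines. A participant reduced for VLS who later has an irAE has had several toxicities, and the most-conservative rule carries no limit to a single cycle. The Investigator decides whether to restart and has the final say on dose. The likely purpose of the restart sentence is only that an irAE does not itself trigger a reduction, and raising a reduced dose would itself be a modification. The routes are also thin: the master protocol reports no VLS in HAMMER and does not expect it, and the Grade 2 ICANS reduction is optional.

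Most of this stands, and it is why the practical risk is small. It does not remove the inconsistency. No text says that Section 6.5.1 governs the irAE restart, and a reader who lets the specific section prevail over the general one reaches the higher dose. The most-conservative rule can be argued not to reach a VLS event resolved cycles earlier. Investigator judgment permits the safe dose without stating it. Section 6.5.1 also asks for Sponsor consultation before departing from stated dose modifications, so a site that keeps the reduced dose could appear to deviate from Section 6.5.4.4.

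**Conclusion.** The point holds as a minor inconsistency in the dosing text. Section 6.5.4.4 contradicts Section 6.5.1 for a participant whose SAR444245 dose was reduced before an irAE hold. This rests on the wording alone and needs no redacted figure. The frequency is unknown and possibly zero. No estimand, confidence interval or sample size changes.

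Three stronger inferences are not supported.

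- A reader might infer that the protocol, taken as a whole, directs sites to re-escalate. It does not: its other provisions lean towards the reduced dose.
- A reader might take 0.13 to 0.26 participants as a ceiling. The inputs come from a different regimen and from an assumed reduction rate, so they cap nothing.
- The amendment summary records that Table 5 text was deleted for consistency with Section 6.5.1, and a reader might infer that it concerned re-escalation. The deleted text is redacted, so nothing about its content can be concluded.

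**What to change.** At the next amendment, replace the restart sentence in Substudy 01 Section 6.5.4.4 with:

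> When restarted, pembrolizumab should be given at its planned dose and SAR444245 at the dose level in use before the irAE (or lower if Table 5, 7 or 8 requires it), on the planned schedule; an irAE alone does not trigger a dose reduction, and a previously reduced SAR444245 dose must not be re-escalated (Section 6.5.1).

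The words in parentheses matter. Without them, a participant whose VLS, CRS or ICANS occurs together with the irAE would be sent back to the earlier, higher dose when the event table calls for a lower one.

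The cost is one sentence. Table 6, pembrolizumab dosing, data collection and the SAP stay as they are, and no separate letter to sites is needed.
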